**Figure 4-1 Study design**

#### 4.1.1 Investigational Treatment, Other Study Treatment, Study Treatment, Supportive Treatment

Investigational treatment in all patients will consist of oral dovitinib 500 mg taken once daily for 5 consecutive days followed by 2 days off repeated every week. Each treatment cycle will be defined as 28 days (4 weeks). In patients not experiencing significant toxicity or relapsed disease, a study-defined maximum number of dovitinib cycles will not be stipulated. Dovitinib will be supplied in the form of 100 mg hard gelatin capsules or film coated tablets.

Standard of care cystoscopy and urine cytology will be performed every 3 months  $\pm$  7 days during the first 12 months of follow-up and per the treating urologist's discretion thereafter. Standard of care tumor biopsy and bladder biopsies will be performed every 3 months  $\pm$  7 days during the first 6 months of follow-up and per the treating urologist's discretion thereafter.

Anti-emetic medications are permitted at the discretion of the treating physician.

Colony stimulating growth factor (i.e. erythropoietin, darbopoeitin, pegfilgrastim, etc.) support is permitted at the discretion of the treating physician.

**Table 4-1 Study drugs**

Study drugs	
Investigational drug	Dovitinib
Standard of Care	Cystoscopy with tumor biopsy, bladder biopsy, urine cytology
Physician discretion	Anti-emetic medications
Physician discretion	Colony stimulating growth factors

#### **4.1.2 Treatment Arms**

This trial is a single-arm non-randomized trial. As such, all patients enrolled will receive dovitinib as outlined in section 4.1.1.

#### **4.2 Definition of End of the Study**

The study will end when all patients have either: 1) Confirmed relapsed disease OR 2) 12-months of follow-up after discontinuing dovitinib in the absence of relapsed disease.

For early stopping rules for the study see section 10.10 Early Stopping Rules.

#### **4.3 Early Study Termination**

The study can be terminated at any time for any reason by the Sponsor Investigator or Novartis, the investigational drug supplier. Should this be necessary, the patient should be seen as soon as possible and treated as described in Section 7 for a prematurely withdrawn patient. The investigator may be informed of additional procedures to be followed in order to ensure that adequate consideration is given to the protection of the patient's interests. The investigator will be responsible for informing IRBs and/or ECs of the early termination of the trial.

### **5 Population**

The investigator or his/her designee must ensure that only patients who meet all the following inclusion and none of the exclusion criteria are offered enrollment in the study.

#### **5.1 Inclusion Criteria**

Patients eligible for inclusion in this study have to **meet all** of the following criteria:

1. Histologically confirmed non-muscle invasive urothelial carcinoma of the bladder defined as Ta, T1, or Tis stage. Tumor staging must be confirmed by TURBT performed within 42 days prior to registration.
2. Presence of either an FGFR3 mutation or FGFR3 over-expression within bladder tumor tissue. Somatic FGFR3 mutations (see Table 1-2) in exons 7, 10, and 15 will be assessed in FFPE tumor tissues by massively parallel sequencing analysis utilizing the Ion Torrent Personal Genome Machine (PGM) and performed in the CLIA-certified Molecular Pathology and Translational Research Laboratory at the Dartmouth Hitchcock Medical Center. FGFR3 over-expression will be assessed by standard IHC analysis performed within the Indiana University Simon Cancer Center Immunohistochemistry (IHC) Core Lab.

NOTE: Patients will initially be allowed to enroll if their tumors demonstrate either an FGFR3 mutation or FGFR3 over-expression. However, a minimum of 10 FGFR3

mutation positive patients will be enrolled at study completion. If 10 patients with tumors that are FGFR3 over-expressors but FGFR3 mutation negative are accrued prior to enrolling 10 FGFR3 mutation positive patients, subsequent enrollment will be restricted to patients with tumors that are FGFR3 mutation positive.

3. Documented BCG-refractory disease defined as failure to achieve a tumor free state after at least 2 prior intravesical treatment courses, one of which must have been intravesical BCG therapy.

**NOTE:** There is no maximum limit on the number of prior BCG therapy courses. In addition, there is no maximum limit on the number of prior non-BCG intravesical therapy courses (i.e. gemcitabine, valrubicin, interferon, mitomycin C, etc.).

4. Medically unfit to undergo cystectomy or electively choosing to forego cystectomy

5. ECOG (WHO) performance status 0 or 1 or 2

6. Age  $\geq$  18 years old

7. Patients must have the following laboratory values:

- White blood cell count (WBC)  $\geq$  3.0 K/mm^3
- Absolute neutrophil count (ANC)  $\geq$  1.5 K/mm^3
- Platelets  $\geq$  100 K/mm^3
- Hemoglobin (Hgb)  $\geq$  9 g/dL
- Serum total bilirubin:  $\leq$  1.5 x ULN
- ALT and AST  $\leq$  3.0 x ULN
- Serum creatinine  $\leq$  1.5 x ULN or serum creatinine  $>1.5 - 3$  x ULN if calculated creatinine clearance (CrCl) is  $\geq$  30 mL/min using the Cockcroft-Gault equation, see formula below:  
$$\text{CrCl} = [140 - \text{age (years)}] \times \text{weight (kg)} / [72 \times \text{serum Cr (mg/dL)}]$$
 (if patient is female multiply the above by 0.85)
- Urine dipstick reading: Negative for proteinuria or, if documentation of +1 (+2 for patients with renal cell carcinoma) results for protein on dipstick reading, then total urinary protein  $\leq$  500 mg and measured creatinine clearance  $\geq$  50 mL/min/1.73m^2 from a 24 hour urine collection

8. Patients who give a written informed consent obtained according to local guidelines

## 5.2 Exclusion Criteria

Patients eligible for this study **must not meet any** of the following criteria:

1. Patients with muscle-invasive (i.e. T2, T3, T4), locally advanced non-resectable, or metastatic urothelial carcinoma as assessed on baseline radiographic imaging obtained within 28 days prior to study registration. The required radiographic imaging includes:
  - a. Abdomen/Pelvis – CT scan
  - b. Chest – chest x-ray or CT scan
2. Patients with concurrent upper urinary tract (i.e. ureter, renal pelvis) non-invasive urothelial carcinoma.

3. Patients with another primary malignancy within 3 years prior to starting study drug, with the exception of adequately treated in-situ carcinoma of the uterine cervix, clinically localized prostate cancer, biochemically relapsed non-metastatic prostate cancer (i.e. PSA only disease), or skin cancer (such as basal cell carcinoma, squamous cell carcinoma, or non-melanomatous skin cancer)
4. Patients who have received the last administration of an anticancer therapy including chemotherapy, immunotherapy, and monoclonal antibodies  $\leq$  4 weeks prior to starting study drug, or who have not recovered from the side effects of such therapy
5. Patients who have received targeted prior VEGFR or FGFR-targeted agents (i.e. sunitinib, pazopanib, sorafenib, bevacizumab, axitinib, etc.).
6. Patients who have had radiotherapy  $\leq$  4 weeks prior to starting study drug, or who have not recovered from radiotherapy toxicities
7. Patients who have undergone major surgery (e.g. intra-thoracic, intra-abdominal or intra-pelvic), open biopsy or significant traumatic injury  $\leq$  4 weeks prior to starting study drug, or patients who have had minor procedures (i.e. TURBT), percutaneous biopsies or placement of vascular access device  $\leq$  1 week prior to starting study drug, or who have not recovered from side effects of such procedure or injury
8. Patients with any of the following concurrent severe and/or uncontrolled medical conditions which could compromise participation in the study:
  - Impaired cardiac function or clinically significant cardiac diseases, including any of the following:
    - a. History or presence of serious uncontrolled ventricular arrhythmias
    - b. Clinically significant resting bradycardia
    - c. LVEF assessed by 2-D echocardiogram (ECHO)  $<$  50% or lower limit of normal (whichever is higher) or multiple gated acquisition scan (MUGA),  $<$  45% or lower limit of normal (whichever is higher)
    - d. Any of the following within 6 months prior to starting study drug: myocardial infarction (MI), severe/unstable angina, Coronary Artery Bypass Graft (CABG), Congestive Heart Failure (CHF), Cerebrovascular Accident (CVA), Transient Ischemic Attack (TIA), Pulmonary Embolism (PE)
    - e. Uncontrolled hypertension defined by a SBP  $\geq$  160 mm Hg and/or DBP  $\geq$  100 mm Hg, with or without anti-hypertensive medication(s)
  - Impairment of gastrointestinal (GI) function or GI disease that may significantly alter the absorption of dovitinib (e.g. ulcerative diseases, uncontrolled nausea, vomiting, diarrhea, malabsorption syndrome, or small bowel resection)
  - Cirrhosis, chronic active hepatitis or chronic persistent hepatitis
  - Known diagnosis of human immunodeficiency virus (HIV) infection (HIV testing is not mandatory)
  - Patients who are currently receiving anticoagulation treatment with therapeutic doses of warfarin. Full-dose anti-coagulation with low molecular weight heparin is permitted.
  - Other concurrent severe and/or uncontrolled concomitant medical conditions (e.g. active or uncontrolled infection, uncontrolled diabetes) that could cause unacceptable safety risks or compromise compliance with the protocol

9. Pregnant or nursing (lactating) women, where pregnancy is defined as the state of a female after conception and until the termination of gestation, confirmed by a positive hCG laboratory test.
10. Women of child-bearing potential, defined as all women physiologically capable of becoming pregnant, unless they are using highly effective methods of contraception (defined below). Highly effective contraception must be used by both sexes (female patients and their *male partners*) *during study treatment and for 30 days after the last dose of study medication*.

Highly effective contraception methods include:

- Total abstinence (when this is in line with the preferred and usual lifestyle of the subject). Periodic abstinence (e.g., calendar, ovulation, symptothermal, post-ovulation methods) and withdrawal are not acceptable methods of contraception
- Female sterilization (have had surgical bilateral oophorectomy with or without hysterectomy) or tubal ligation at least six weeks before taking study treatment. In case of oophorectomy alone, only when the reproductive status of the woman has been confirmed by follow up hormone level assessment
- Combination of the following (a+b):
  - a. Placement of an intrauterine device (IUD) or intrauterine system (IUS)
  - b. Barrier methods of contraception: Condom or Occlusive cap (diaphragm or cervical/vault caps) with spermicidal foam/gel/film/cream/vaginal suppository

Oral, implantable, or injectable hormone contraceptives may be affected by cytochrome P450 interactions, and are therefore not considered effective for this study

Women of child-bearing potential (sexually mature women) who have not undergone a hysterectomy or who have not been naturally postmenopausal for at least 12 consecutive months (i.e., who has had menses any time in the preceding 12 consecutive months), must have a negative serum pregnancy test  $\leq$  14 days prior to starting study drug.

11. Fertile males not willing to use contraception. Fertile males must use condom with spermicide. Highly effective contraception, as defined above, must be used by both sexes (male patients and their female partners) during study treatment and for 90 days after the last dose of study medication and should not father a child in this period. A condom is required to be used also by vasectomized men in order to prevent delivery of the drug via seminal fluid.
12. Patients unwilling or unable to comply with the protocol

## 6 Treatment

### 6.1 Treating the Patient

The investigator needs to instruct the patient to take the study drug dovitinib as per protocol. All dosages prescribed and dispensed to the patient and all dose changes during the study must be recorded on a drug accountability form (see study procedure manual [SPM] for example) and entered into the EDC system.

#### 6.1.1 Administration

Dovitinib will be dosed on a flat scale of 500 mg (i.e. 5 x 100 mg per capsule/tablet) on a 5 days on/2 days off dosing schedule. Dovitinib may be taken with or without food.

- If a patient forgets to take dovitinib at the routinely scheduled time, then the patient can take dovitinib within 6 hours of the routinely scheduled time. If a dose is not taken within this 6 hour window, it should be skipped. If a patient's dose is skipped on a given day, then the patient should resume dovitinib at the routinely scheduled time the next morning, provided it is a scheduled day of dosing.
- If a patient routinely takes his/her dose of dovitinib in the evening, and forgets to take dovitinib as scheduled, then the patient can take dovitinib within 6 hours of the routinely scheduled time. If a dose is not taken within this 6 hour window, it should be skipped. The patient should resume dovitinib at the routinely scheduled time the next evening, provided it is a scheduled day of dosing.

## 6.1.2 Dosing and Treatment Schedule

**Table 6-1 Dosing and treatment schedule**

Study drugs	Pharmaceutical form and route of administration	Dose	Frequency
Dovitinib	Capsule/tablet for oral use	500 mg	5 days on/2 days off

## 6.1.3 Dose Modification and Dose Delay

For patients who do not tolerate the protocol-specified dosing schedule, dose adjustments are permitted in order to allow the patient to continue the study drug. The following guidelines need to be applied:

These changes must be recorded in the eCRF.

**Table 6-2 Dose reduction steps for dovitinib**

Dose reduction*			
	Starting dose level - 0	Dose level - 1	Dose level - 2
Dovitinib	500 mg	400 mg	300 mg**
*Dose reduction should be based on the worst toxicity demonstrated at the last dose.			
**Dose reduction below 300 mg is not allowed.			

## 6.1.4 Treatment Interruption and Treatment Discontinuation

Toxicity intensity a	Dose modification b, c
Cardiovascular	
Hypertension	Treatment-emergent hypertension should be treated as per standard cardiology practice. Recommended agents for the management of blood pressure elevations on dovitinib include angiotensin-converting enzyme inhibitors and calcium channel blockers.
SBP < 160 mmHg and/or DBP < 100 mm Hg, with or without anti-hypertensive medication	Maintain dose level
SBP ≥ 160 mmHg and/or DBP ≥ 100 mm Hg, with or without anti-hypertensive medication, but not immediately life-threatening	Delay the study treatment and initiate/intensify antihypertensive therapy. Dovitinib may be restarted in conjunction with standard anti-hypertensive medication if BP is controlled (i.e. BP < 160/100 mmHg). Once BP is controlled after suspending dovitinib, maintain dose level or ↓ 1 dose level at the discretion of the investigator.
Life-threatening consequences (e.g., malignant hypertension, transient or permanent neurologic deficit, hypertensive crisis); urgent intervention	Discontinue study treatment permanently

Toxicity intensity a	Dose modification b, c
indicated	
Left ventricular systolic dysfunction	
Left ventricular ejection fraction (LVEF) $\geq$ 50%/LLN (ECHO), or $\geq$ 45%/LLN (MUGA)	Maintain dose level
LVEF $<$ 50%/LLN (ECHO), or $<$ 45%/LLN (MUGA), or Symptomatic due to drop in ejection fraction responsive to intervention	Delay study treatment until resolved to $\geq$ 50%/LLN (ECHO) or $\geq$ 45%/LLN (MUGA), then $\downarrow$ 1 dose level
Refractory or poorly controlled heart failure due to drop in ejection fraction; intervention such as ventricular assist device, intravenous vasopressor support or heart transplant indicated	Discontinue study treatment
Other cardiovascular	
Grade 1	Maintain dose level
Grade 2	Maintain dose level If asymptomatic decrease of LVEF by absolute value of 20% and to $<$ LLN, delay study treatment until resolved to $\leq$ grade 1, then $\downarrow$ 1 dose level
Grade 3	Delay study treatment until resolved to $\leq$ grade 1, then $\downarrow$ 1 dose level
Grade 4	Discontinue study treatment
Gastrointestinal	
Diarrhea	At the first sign of abdominal cramping, loose stools, or onset of diarrhea, it is recommended that the patient be treated according to institutional standard of care
Grade 1 (despite maximal anti-diarrheal medication)	Maintain dose level
Grade 2 (despite maximal anti-diarrheal medication)	Delay study treatment, until resolved to $\leq$ grade 1, then re-start at the current dose level If diarrhea returns as $\geq$ grade 2, then suspend dose until resolved to $\leq$ grade 1, then $\downarrow$ 1 dose level
Grade 3/4 (despite maximal anti-diarrheal medication)	Delay study treatment until resolved to $\leq$ grade 1, then $\downarrow$ 1 dose level
Nausea	Suspend dose for CTCAE grade 2-3 nausea only if it could not be controlled despite the use of standard anti-emetics.
Grade 1 (despite standard anti-emetics)	Maintain dose level
Grade 2 (despite standard anti-emetics)	Delay study treatment, until resolved to $\leq$ grade 1, and then re-start at the current dose level. If nausea returns as $\geq$ grade 2, then suspend dose until resolved to $\leq$ grade 1, then $\downarrow$ 1 dose level.
Grade 3 (despite standard anti-emetics)	Delay study treatment until resolved to $\leq$ grade 1, then $\downarrow$ 1 dose level
Vomiting	Suspend dose for CTCAE grade 2-4 vomiting only if it could not be controlled despite the use of standard anti-emetics.
Grade 1 (despite standard anti-emetics)	Maintain dose level
Grade 2 (despite standard anti-emetics)	Delay study treatment, until resolved to $\leq$ grade 1, and then re-start at the current dose level. If nausea returns as $\geq$ grade 2, then suspend dose until resolved to $\leq$ grade 1, then $\downarrow$ 1 dose level.
Grade 3/4 (despite standard anti-emetics)	Delay study treatment until resolved to $\leq$ grade 1, then $\downarrow$ 1 dose level
Hematologic	

Toxicity intensity a	Dose modification b, c
Febrile neutropenia (Grade 3 or 4) (Per protocol) fever of unknown origin without clinically or microbiologically documented infection (ANC <1.0 x 10  /L, fever ≥ 38.5°C)	Delay study treatment until resolved, then ↓ 1 dose level
≥ Grade 3 anemia judged to be a hemolytic process secondary to study treatment	Discontinue study treatment.
≥ Grade 3 lymphopenia considered clinically significant	Requires dose interruption until resolved to ≤ grade 1, then ↓ dose level.
Neutropenia/Neutrophil count decreased	
Grade 1 or 2	Maintain dose level
Grade 3 Grade 4	Delay study treatment until resolved to ≤ grade 2, then: If resolved by ≤ 7 days after suspending dovitinib, maintain dose level If resolved by > 7 days after suspending dovitinib, ↓ 1 dose level
Thrombocytopenia/Platelet count decreased	
Grade 1 or 2	Maintain dose level
Grade 3	Delay study treatment until resolved to ≤ grade 1, then: If resolved by ≤ 7 days after suspending dovitinib, maintain dose level If resolved by > 7 days after suspending dovitinib, ↓ 1 dose level
Grade 4	Delay study treatment until resolved to ≤ grade 1, then ↓ 1 dose level
Hepatic	
≥ grade 3 alkaline phosphatase or GGT	Isolated values of ≥ grade 3 alkaline phosphatase or GGT values will NOT require dose interruption.
ALT or AST	
≤ 3.0 x ULN	Maintain dose level with LFTs e monitored as per protocol.
> 3.0 to ≤ 5.0 x ULN, without bilirubin elevation to > 2.0 x ULN	Maintain dose level with weekly monitoring of LFTs e , or more frequently if clinically indicated, until resolved to ≤ grade 1 or baseline.
> 5.0 x ULN	Delay study treatment until resolved to ≤ grade 1 or baseline, then ↓ 1 dose level. Monitor LFTs e weekly, or more frequently if clinically indicated, for 8 weeks; then, every 2 weeks for 4 weeks; then, every 4 weeks as per protocol. Following re-introduction of dovitinib, if ALT or AST elevations > 3 x ULN recur as assessed on 2 separate measurements no more than 1 week apart, then study treatment should be permanently discontinued. If study treatment is permanently discontinued, then patients should be monitored weekly (including LFTs e ), or more frequently if clinically indicated, until AST or ALT have resolved to ≤ grade 1 or stabilization (i.e., no CTCAE grade change over 4 weeks).
Total bilirubin	
≤ 1.5 x ULN	Maintain dose level with LFTs e monitored as per protocol.
> 1.5 to 3.0 x ULN with ALT or AST ≤ 3.0 x ULN	Maintain dose level with LFTs e monitored as per protocol.

Toxicity intensity a	Dose modification b, c
> 3.0 x ULN	
Discontinue study treatment permanently.
 
Patients should be monitored weekly (including LFTse), or more frequently if clinically indicated, until total bilirubin has resolved to ≤ grade 1 or stabilization (i.e., no CTCAE grade change over 4 weeks).
 
Note: If grade 3 or grade 4 hyperbilirubinemia is due to the indirect component only, and hemolysis as the etiology has been ruled out as per institutional guidelines (e.g., review of peripheral blood smear and haptoglobin determination), then ↓ 1 dose level and continue treatment at the discretion of the investigator.

ALT or AST, and concurrent Bilirubin elevation	
ALT or AST > 3.0 x ULN AND Total Bilirubin > 2.0 x ULN	
Discontinue study treatment permanently.
 
Patients should be monitored weekly (including LFTse), or more frequently if clinically indicated, until ALT/AST and total bilirubin have resolved to ≤ grade 1 or stabilization (i.e., no CTCAE grade change over 4 weeks).

Renal	
Serum creatinine	
Grade 1 or 2	Maintain dose level
Grade 3	Delay study treatment until resolved to ≤ grade 1 or baseline, then ↓ 1 dose level
Grade 4	Discontinue study treatment
Amylase and/or lipase elevations	
Asymptomatic Grade 1 or 2	Maintain dose level
Asymptomatic Grade 3 or 4	Patients who develop grade 3 or 4 hyperlipasemia or hyperamylasemia without clinical or other evidence of pancreatitis may continue study medication without interruption
Pancreatitis	
Grade 2	Maintain dose level
Grade 3 or 4	Discontinue study treatment
Hand-foot syndrome	
Grade 1 or 2	Maintain dose level
Grade 3	Delay study treatment until resolved to ≤ grade 1 then ↓ 1 dose level
Grade 4	Discontinue study treatment
Other clinically significant adverse events	
Grade 1 or 2	Maintain dose level
Grade 3 (except hyperlipidemia d )	Delay study treatment until resolved to ≤ grade 1 or baseline, then maintain dose level or ↓ 1 dose level at the discretion of the investigator
Grade 4	Delay study treatment until resolved to ≤ grade 1 or baseline, then ↓ 1 dose level or discontinue dovitinib at the discretion of the investigator
All dose modifications should be based on the worst preceding toxicity.	
a Common Terminology Criteria for Adverse Events (CTCAE) v4.03	
b Patients are allowed two dose reductions: a dose reduction to 400 mg from 500 mg, and, if necessary, a dose reduction to 300 mg from 400 mg.	
c If a patient requires a dose interruption of > 14 days starting from the first day a dose was missed, then the patient must be discontinued from the study. Patients who discontinue the study for a study related adverse	

Toxicity intensity a	Dose modification b, c
event including an abnormal laboratory value must be followed at least once a week for 4 weeks and subsequently at 4 week intervals until resolution or stabilization of the event, whichever comes first.	
d Grade 3 hyperlipidemia (hypercholesterolemia and/or hypertriglyceridemia) should be managed using standard therapies. Fluvastatin and Rosuvastatin may have potential of drug to drug interactions. If these statins are prescribed, close clinical monitoring including serum lipids is required since dovitinib could reduce the exposure of statins. Statins should be prescribed according to product label/data sheets for HMG-CoA reductase inhibitors. Treatment of hyperlipidemia should take into account the pre-treatment status and dietary habits. Blood tests to monitor hyperlipidemia must be taken in the fasting state. Grade 2 or higher hypercholesterolemia ( $>300$ mg/dL or $7.75$ mmol/L) or Grade 2 or higher hypertriglyceridemia ( $>2.5 \times$ ULN) should be treated with fibrate, or appropriate lipid-lowering medication in addition to diet.	
e LFTs include albumin, ALT, AST, total bilirubin (fractionated [direct and indirect], if total bilirubin $> 2.0 \times$ ULN), alkaline phosphatase (fractionated [quantification of isoenzymes], if alkaline phosphatase $\geq$ Grade 2), and GGT.	

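### The grade 2 vomiting row of the Section 6.1.4 dose table names nausea as its recurrence trigger, so vomiting that returns at grade 2 without grade 2 nausea has no prescribed dose reduction

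*Combined protocol and SAP*

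**What the plan says.** Section 6.1.3 introduces the dose rules by saying that, for patients who do not tolerate the schedule, "dose adjustments are permitted in order to allow the patient to continue the study drug", and adds: "The following guidelines need to be applied". The rules themselves are in the table in Section 6.1.4.

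The gastrointestinal part of that table has separate blocks for diarrhea, nausea and vomiting. The vomiting block opens with its own scope statement: "Suspend dose for CTCAE grade 2-4 vomiting only if it could not be controlled despite the use of standard anti-emetics". Its grade 2 row tells the site to hold dovitinib until the event falls to grade 1 or lower, "and then re-start at the current dose level. If nausea returns as" grade 2 or higher, at which point the dose is held again and then lowered one level. The same words appear in the grade 2 row of the nausea block, where they are correct. The matching diarrhea row reads "then re-start at the current dose level If diarrhea returns as" grade 2 or higher.

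Vomiting at grade 3 or 4 has its own row, which calls for a hold and then a one-level reduction.

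**The concern.** A recurrence rule needs to be triggered by recurrence of the event it manages. Here the vomiting rule is triggered by nausea. A site that follows the printed text would have no instruction to lower the dose for a patient whose grade 2 vomiting resolves and then returns at grade 2 while nausea stays below grade 2. The row's opening instruction would simply apply again: hold, then restart at the same dose.

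The row is likely to be used. Section 1.2.2 lists vomiting among the dose-limiting toxicities and the most commonly reported adverse events, and says most of these gastrointestinal events were grade 1 or 2. Grade 2 is the lowest vomiting grade at which the table acts. The trial is multi-center, and Section 12 says that no authorized deviations are permitted, so sites should not have to choose between the printed word and the inferred one.

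**Working it through.** The plan gives no figure on this point, so there is none to reproduce. The check compares the parallel rows, then looks for any other text that supplies the missing trigger.

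**Step 1. Parallel grade 2 rows in Section 6.1.4**

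| Block | First occurrence at grade 2 | Event whose return triggers the reduction | Own event? |
|---|---|---|---|
| Diarrhea | Hold, restart at same dose | Diarrhea, grade 2 or higher | Yes |
| Nausea | Hold, restart at same dose | Nausea, grade 2 or higher | Yes |
| Vomiting | Hold, restart at same dose | Nausea, grade 2 or higher | No |

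The sentence in the vomiting row is complete, so this is not a broken table or redacted text.

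**Step 2. Other text that might fill the gap**

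- *Vomiting, grade 3/4 row:* prescribes a reduction, but not for recurrence at grade 2.
- *Section 6.1.3:* permits adjustments and sets no trigger.
- *Table 6-2 footnote and the line at the foot of the Section 6.1.4 table:* both base dose changes on the worst toxicity. In this case the worst toxicity is grade 2 vomiting, which leads back to the same row.
- *Note b to the table:* "Patients are allowed two dose reductions: a dose reduction to 400 mg from 500 mg", and then a further one to 300 mg. This caps the number of reductions and does not say when to make one.
- *Row for other clinically significant adverse events:* at grade 1 or 2 the dose is maintained, so it does not help.
- *Investigator discretion:* the table states it where it is intended. The hypertension row, for example, offers the same dose or a reduction of "1 dose level at the discretion of the investigator". The grade 2 vomiting row has no such clause.

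None of these prescribes the step down.

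**Step 3. Extent of the gap in the rule**

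Take a patient already held once for grade 2 vomiting whose uncontrolled vomiting then recurs. Cross vomiting grade at recurrence (2, 3, 4) with concurrent nausea grade (0, 1, 2, 3): 3 × 4 = 12 combinations. Any nausea of grade 2 or higher is counted as having returned, which is the reading most favourable to the text.

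- Vomiting grade 3 or 4: 2 × 4 = 8, reduction prescribed by the grade 3/4 row.
- Vomiting grade 2 with nausea grade 2 or 3: 2, reduction prescribed by the row as printed.
- Vomiting grade 2 with nausea grade 0 or 1: 2, no reduction prescribed.

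As printed, the reduction is prescribed in 8 + 2 = 10 of 12; with the corrected word it is 12 of 12. The count only locates the gap. The combinations are not equally likely and are not patient frequencies.

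**The case against.** The strongest reply is that the error corrects itself in context. The row sits under a vomiting heading. What returns must be what resolved, and that is vomiting; in a patient who never had nausea, nausea cannot return. The two neighbouring rows show the intended pattern, so a careful reader would supply the right word.

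Nor is the patient left exposed on the literal reading. Treatment is held at each recurrence, and Section 6.1.3 allows a discretionary reduction. Section 6.2.6 allows prophylactic anti-emetics. Note c to the table requires discontinuation when an interruption exceeds 14 days. Section 7.6 lets the physician stop dovitinib for toxicity (item 3) and the patient stop at any time (item 4). What is missing is a mandatory step where a discretionary one already exists.

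All of this stands, and it is why the point ranks low. It does not make the text right: a dosing rule that sites are told to apply should not need inference, and a permitted reduction may be made at one site and not at another.

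**Conclusion.** The concern holds as a minor but real error in an operative safety rule. Its extent is one situation: vomiting that recurs at exactly grade 2, uncontrolled by anti-emetics, with nausea at grade 0 or 1. There the apparent intent is a reduction from 500 to 400 mg, or from 400 to 300 mg, and the printed row prescribes none.

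The conclusion rests on reading the row literally and on taking the diarrhea and nausea rows as evidence of intent. How many patients would be affected cannot be derived from the documents. There is no effect on the 6-month complete response endpoint, the sample size of 20, the Agresti-Coull bound or the early stopping rule. Correcting it is optional for the statistics and worthwhile for consistent dosing across sites.

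**What to change.** In Section 6.1.4, in the grade 2 row under Vomiting, change the recurrence trigger from nausea to vomiting. Leave the rest of that row and the whole nausea row as they are. The change is one word and can go into the next amendment. It adds no procedure, visit or data item.
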